4.4 Schedule of Events

*A CT scan post-op is standard of care in clinical practice to document fusion. The CT scan will be done at 6 months post-op rather than the usual 12 months. Cost will be covered by study sponsor. **Optional time point (when available).

4.5 Follow-Up Assessments

Subjects will be asked to return postoperatively at 3 months (\pm 1 week), 6 months (\pm 2 weeks), and 12 months (\pm 1 month) for a clinical and radiographic exam. An additional visit at 24 months may be scheduled at the request of either the physician or the subject. The following data will be recorded on the Case Report

Forms (CRFs) and in addition, electronic data entry will be employed via an Internet connection when possible using REDCap.

Clinical assessment: The investigator will carry out a clinical examination at the 3, 6, 12, and when available, 24-month visits to assess:

- subject compliance with postoperative care instructions,
- ability to return to work and normal activity, and
- any procedure related or device related adverse events since discharge from the hospital
- review of medication usage
- progress towards fusion consolidation
- Neurological status All subjects' neurological status will be assessed and recorded as intact or not intact, based upon the investigator's motor, sensory and reflex evaluations.

Subject self-assessment (Patient completed forms):

• Each subject will be asked to complete a follow-up Oswestry Disability Index (ODI) form and a Back and Leg Pain VAS form at each follow-up visit.

Radiographic assessment: Each subject will undergo AP, lateral and flexion/extension radiographs at the 3, 6, 12, and when available, 24-month visits as well as a CT scan at 6 months to assess:

• integrity of the device and graft, with observation for events such as rod, hook, screw and/or spacer (if applicable) migration or subsidence, hardware fracture, and progress towards fusion consolidation

Findings from any additional imaging studies deemed necessary by the investigator will be recorded and reported with study results.

4.6 Independent Radiographic Assessment

An independent radiographic analysis will be performed to evaluate all images and assess subjects' radiographic status. The independent radiographer will receive deidentified disks and will not have access to any personally identifiable information. The following quantitative and qualitative assessments will be performed.

Fusion Determination

Fusion will be assessed by an independent radiographer when data collection is complete. X-rays at each visit and a lumbar CT at 6 months will be evaluated for fusion determination. Interbody fusion will be graded by the method of Brantigan and Steffee as modified to describe the Fraser definition of locked pseudoarthrosis (BSF scale) (Santos et al., 2003). The grading system is as follows:

- BSF-1: Radiographical pseudarthrosis
- BSF-2: Radiogaphical locked pseudarthrosis
- BSF-3: Radiographical fusion

Radiographic Success: Radiographic success is defined by radiographical fusion (BSF-3) presenting bone bridges within at least half of the fusion area with at least the density originally achieved at surgery.

Radiographic Failure: Radiographic failure is defined by radiographical pseudarthrosis (BSF-1 or -2)

X-rays will be uploaded into the REDCap as a JPEG image at each subject visit.

4.7 Success Criteria

4.7.1 **Primary Measure of Effectiveness**

A subject will be considered a success if fusion is a Grade BSF-3 at 6 months. The primary outcome measure of effectiveness will be determined by the fusion rate at 6 months post-operatively in subjects implanted with either titanium cage as compared to the PEEK cage.

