4.2 Randomization

All subjects will be randomized in the trial to receive either the Nexxt Spine Nexxt MatrixxTM 3D-printed titanium cage or the HonourTM PEEK cage supplemented with a pedicle screw system and milled local autograft bone. Subject randomization will be stratified according to smoking status. Subjects will be blinded to their group status for the duration of the study assessments and procedures (12 months post-operatively).

4.3 **Perioperative and Postoperative Management**

Surgeons will perform combined interbody and posterolateral lumbar fusion utilizing either Nexxt MatrixxTM or PEEK cages supplemented with a pedicle screw system cleared for fusion and milled local autograft bone (per customary protocol).

Data will be collected during and immediately after the surgery according to the parameters described by the Nexxt Matrixx[™] IF/PLF CRFs. This includes: diagnosis, duration of surgery, blood loss, OR time, length of hospital stay, instrumentation used, type of procedure, and surgical level(s). In addition, all intra-operative complications (e.g. excessive blood loss, hematoma, vascular injury, etc.) will be reported and recorded as a complication on the CRF.

Intra-operative (after hardware installation is completed) or immediate postoperative x-rays will be obtained. Postoperative care will follow the standard of care at each institution for subjects who undergo fusion procedures.

Postoperative care is extremely important. The subject should be warned that noncompliance with postoperative instructions could lead to breakage of the pedicle screw system and/or possible migration requiring revision surgery to remove the pedicle screw system.

Screening/	Procedure	3 months	6 months	12 months	24 months
Enrollment		(± 7 days)	(± 14 days)	(± 30 days)	(± 60 days)
procedure)					
Х					
Х					
Х					
Х	Х	Х	Х	Х	X**
	Х				
Х		Х	Х	Х	X**
X		Х	X	Х	X**
X		Х	X	Х	X**
			X*		
Х	Х	Х	Х	Х	X**
	Enrollment (-60 days of procedure) X X X X X X X X X X X X	Enrollment (-60 days of procedure) X X X X X X X X X X X X X X X	Enrollment (-60 days of procedure)(± 7 days)X	Enrollment (-60 days of procedure)(± 7 days)(± 14 days)XXX	Enrollment (-60 days of procedure) $(\pm 7 days)$ $(\pm 14 days)$ $(\pm 30 days)$ X </td

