4.8 Subject Withdrawal

It is recognized that the subject's participation in this trial is entirely voluntary, and that she/he may refuse to participate and may withdraw from participation at any time without jeopardy to any future medical care. It is also recognized that the investigator, at his/her discretion, may withdraw a subject from this study based upon his/her professional judgment.

Other Conditions for Withdrawal:

Any subject who develops a severe concurrent medical illness during the trial should be withdrawn. This type of illness is defined as any illness that would hinder the subject's ability to return for scheduled follow-up appointments. Such a withdrawal will not be counted for the purposes of determining success or failure.

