5 COMPLICATIONS

In addition to the standard operating procedures for reporting complications per hospital/physician protocol, all clinical events, including both observed or volunteered problems, complaints, symptoms, physical signs or disease which either occur during the study, having been absent at baseline, or, if present at baseline, appear to worsen during the clinical outcomes collection study are to be recorded as complications in the subject's medical record and on the appropriate case report form.

Complications reported in the literature as most commonly associated with interbody and posterolateral lumbar fusion procedures include, but are not limited to, infection, nerve damage, blood clots, blood loss, and bowel and bladder problems, along with complications associated with anesthesia. A potential risk inherent to spinal fusion is failure of the vertebral bone and graft to properly fuse, a condition that may require additional surgery.

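### Primary success rests on the 6-month BSF grade alone, so a subject whose cage, graft or fixation was revised at an index level before 6 months can still count as a success

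*Combined protocol and SAP*

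**What the plan says.** Section 4.7.1 (Primary Measure of Effectiveness) sets a single condition for success: "A subject will be considered a success if fusion is a Grade BSF-3 at 6 months". It then compares the "fusion rate at 6 months post-operatively in subjects implanted with either titanium cage as compared to the PEEK cage".

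Section 4.6 (Independent Radiographic Assessment) also works from the grade alone: "Radiographic success is defined by radiographical fusion (BSF-3) presenting bone bridges within at least half of the fusion area", with a further condition on density. Grades BSF-1 and BSF-2 are radiographic failures. Neither section mentions re-operation.

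The protocol does expect that some subjects may need more surgery. Section 4.3 (Perioperative and Postoperative Management) warns of "possible migration requiring revision surgery to remove the pedicle screw system". Section 5 (Complications) names as an inherent risk "failure of the vertebral bone and graft to properly fuse, a condition that may require additional surgery".

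Only one event after enrolment has a stated consequence for the outcome. In Section 4.8 (Subject Withdrawal), for withdrawal because of severe concurrent illness, "Such a withdrawal will not be counted for the purposes of determining success or failure". The same section lets the investigator act at discretion (he or she "may withdraw a subject from this study based upon his/her professional judgment"), but does not link this to revision or say how such a subject counts. Section 6 (Statistical Analysis Plan) defines no analysis set and no rule for events after surgery.

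**The concern.** The trial asks whether one cage yields fusion more often than the other. A fusion seen only after the construct was surgically altered is not clean evidence for the assigned cage. The alteration may be a replaced or repositioned cage, added graft, or revised fixation. The success rule treats that subject exactly like one who fused after a single operation.

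Such a subject may be one of the poorer results in the arm, yet is entered as a success. With small arms, a few of these can shift the comparison visibly. Section 6 also allows enrolment to stop if an interim look shows a statistical difference, and at that point each subject weighs more. If the question is left until data are graded, the choice of how to count these subjects could be made with the results in view.

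**Working it through.** **Step 1. Does any provision remove or reclassify a revised subject?**

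| Section | What it settles | Effect on a revised subject graded BSF-3 at 6 months |
|---|---|---|
| 4.7.1 | Success is BSF-3 at 6 months | Success |
| 4.6 | Radiographic success and failure set by BSF grade | Success |
| 4.3 and 5 | Further surgery is foreseen | No outcome rule |
| 4.8 | Withdrawal for severe illness is not counted; discretionary withdrawal is allowed | Not tied to revision |
| 6 | No analysis set or event handling | None |

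Nothing overrides the grade. Section 4.6 has the images read de-identified after data collection is complete, and does not direct that surgical history be given to the reader.

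**Step 2. Which arm gets the credit?** If the cage stays in place (a screw or rod revision, for example), the success goes to that cage. If the cage is exchanged, the phrase about subjects implanted with each cage could mean the first or the later device, and no analysis set decides between them.

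**Step 3. Weight of one subject.** Section 3.1 gives up to 70 subjects, 35 per group. One reclassified subject moves the arm rate by 1/35 = 2.9 points, two by 2/35 = 5.7, three by 3/35 = 8.6.

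At half accrual (70/2 = 35 subjects, so 17 or 18 per arm if all are assessable) one subject moves a rate by 1/18 = 5.6 to 1/17 = 5.9 points.

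**Step 4. Effect on the comparison.** The plan names no test and gives no expected rates, so there is no figure of its own to reproduce. The counts below are assumed, and the test is a two-sided Fisher exact test with 35 per arm.

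| Scenario | Titanium | PEEK | Difference (points) | p |
|---|---|---|---|---|
| Grade-only rule | 33 | 27 | 6/35 = 17.1 | 0.084 |
| One PEEK success reclassified | 33 | 26 | 7/35 = 20.0 | 0.045 |
| Two PEEK successes reclassified | 33 | 25 | 8/35 = 22.9 | 0.023 |
| Two titanium successes reclassified | 31 | 27 | 4/35 = 11.4 | 0.34 |
| One in each arm reclassified | 32 | 26 | 6/35 = 17.1 | 0.11 |

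A second starting point shows loss of significance: 32 v 24 gives p = 0.034, and reclassifying one titanium success (31 v 24) gives p = 0.078. The shift can go either way.

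**Step 5. How likely is any such event?** The documents give no revision risk. With r the assumed risk of index-level revision before 6 months, the expected number per arm is 35r and the chance of at least one among 70 is 1 − (1 − r)^70.

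| Assumed r | Expected per arm | Chance of at least one in 70 |
|---|---|---|
| 1% | 0.35 | 51% |
| 2% | 0.7 | 76% |
| 5% | 1.75 | 97% |
| 8% | 2.8 | 99.7% |

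These are upper limits for the problem cases, because they count every revision and not only those followed by BSF-3 at 6 months.

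**The case against.** **The endpoint is radiographic.** Fusion grade regardless of re-operation is a legitimate treatment-policy estimand; counting revision as non-success is a composite one. The documents do not commit to either. This stands as a reason to keep the grade-only result as a sensitivity analysis. It does not support leaving the choice unstated, since the comparison is meant to be between cages.

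**The text is silent rather than contradictory.** That is true: no two sections conflict. But the silence sits beside an explicit rule that yields a classification when followed, so the consequence is more than missing detail.

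**The pathway may be rare.** A subject must need revision, have it, and then show bridging over at least half of the fusion area, all by 6 months (± 14 days). The surgery described in Section 4.3 is removal of the screw system in the context of non-compliance, not cage failure, and Section 5 gives no timing. An investigator might also withdraw such a subject, although nothing requires it. All of this stands and limits the expected size.

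**A reader might infer that the rule pulls the difference towards zero or favours the worse cage.** The documents do not support that. It would hold only if revised subjects graded BSF-3 were concentrated in the arm with the lower rate, and no revision figures by arm are given.

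**A reader might also infer that the first cage implanted always takes the credit.** That follows only when the cage is left in place.

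**Counting every index-level re-operation as a non-success would be too broad.** It would include a haematoma evacuation or a wound washout with the construct intact, and so create a different misclassification. This stands, and the fix is limited accordingly.

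**Conclusion.** The point holds in limited form. Section 4.7.1 as written counts as a success any subject graded BSF-3 at 6 months, including one whose cage, graft or fixation was surgically altered at an index level beforehand. It leaves the arm unsettled if the cage was exchanged.

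The firm figure is 2.9 points on an arm's rate per affected subject, assuming the full 35 per arm are analysed. The number of such subjects is unknown and probably small. The direction of the effect on the comparison is also unknown. The p-values rest on assumed counts and an assumed test; they show only that one or two subjects can matter, in either direction. The change should be made before images are graded, because it is cheap and removes a choice that could otherwise depend on the results.

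**What to change.** Add to Section 4.7.1, for the primary analysis:

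- A subject is a non-success in the randomised arm, whatever the later BSF grade, if before the 6-month assessment index-level surgery removes, replaces or repositions the cage, adds graft, or revises, removes or supplements the fixation.
- A subject whose re-operation leaves the construct and graft unchanged (haematoma evacuation or wound washout, for example) keeps the BSF grade.
- Counts of both kinds of re-operation are reported by arm.
- The grade-only rule is repeated as a sensitivity analysis.

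This concerns outcome classification only and changes nothing in clinical care. The cost is a short addition to the text and a check of operative records to sort re-operations into the two kinds. Section 5 already requires clinical events to be recorded as complications, but the case report forms are not in the supplied text, so whether they hold enough detail should be confirmed. The stated fusion rate may fall slightly.

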3 TRIAL DESIGN

3.1 Design

The randomized controlled trial will prospectively evaluate the safety and efficacy of the Nexxt Matrixx[™] System titanium implant supplemented with a pedicle screw system as compared to a representative PEEK cage currently used in routine fashion for lumbar interbody fusion procedures. This study will capture clinical and radiographic outcomes on patients up to 2 years post operatively. Both cages will be used in conjunction with milled local autograft bone generated as part of the spinal fusion procedure (no iliac crest autograft will be utilized).

This single centered study will enroll up to 70 subjects (n = 35 per group), with subjects followed for a minimum of 12 months post-surgery. All subjects enrolled in the study will be recruited from a pool of subjects eligible for combined interbody/posterolateral lumbar fusion surgery. The inclusion/exclusion criteria are listed below.

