4 STUDY PROCEDURE

4.1 Screening Assessments

4.1.1 Informed Consent

Subjects will be provided with an informed consent and will be given ample opportunity to review the consent and ask questions. The signed informed consent will be obtained before any study specific procedures, that are not part of the investigator's standard of care begin. A copy of the informed consent will be given to the subject. All subjects who meet all of the entry criteria will be considered for inclusion in this trial. Any subject meeting any of the exclusion criteria will be excluded from the trial.

All subjects who have agreed to participate in this study, have signed the informed consent and who meet the inclusion/exclusion criteria will be considered enrolled and assigned a subject ID number. Once a Subject ID number has been issued, it cannot be reassigned or used for another subject.

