6 STATISTICAL ANALYSIS PLAN

Statistical analyses will be performed as deemed appropriate to evaluate fusion outcomes across the groups.

An interim analysis may be performed once, at minimum, half of the subject accrual is met. In the case early findings show a statistical difference between the two studied cages, enrollment will cease as investigators are unlikely to maintain clinical equipoise to continue to randomize patients. Similarly, if the interim analysis suggests it is unlikely the study will achieve statistical significance, the investigators may choose to close the trial early for futility. Currently enrolled subjects will be followed throughout the remainder of the study, up to 12 months post-surgery.

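### Section 4.7.1 words the primary comparison by the cage implanted, and nothing in the plan says subjects are analysed as randomised; a short rewording would settle it

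*Combined protocol and SAP*

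**What the plan says.** - **Endpoint (Section 4.7.1).** At subject level, "A subject will be considered a success if fusion is a Grade BSF-3 at 6 months". The comparison is then the "fusion rate at 6 months post-operatively in subjects implanted with either titanium cage as compared to the PEEK cage". This is the only sentence in the plan that says who is compared with whom on the primary endpoint.
- **Randomisation (Section 4.2).** "All subjects will be randomized in the trial to receive either the Nexxt Spine" Nexxt Matrixx titanium cage or the Honour PEEK cage, stratified by smoking status. The section describes blinding of subjects only. It gives no rule for a subject who does not receive the assigned cage.
- **Enrolment (Section 4.1.1).** Subjects who have agreed to take part, "have signed the informed consent and who meet the inclusion/exclusion criteria will be considered enrolled and assigned a subject ID number". Enrolment therefore comes before surgery and before any cage is implanted.
- **Analysis (Section 6).** "Statistical analyses will be performed as deemed appropriate to evaluate fusion outcomes across the groups". No analysis population is named.
- **Removal from the count (Section 4.8).** For withdrawal because of severe concurrent illness, "Such a withdrawal will not be counted for the purposes of determining success or failure". This is the only stated rule that takes a subject out of the success or failure count. It does not deal with a switched cage or with no cage.
- **Device (Section 2.2).** Procedures cover one or two levels, and the text presumes that every enrolled subject has one of the two study cages at each level.

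**The concern.** Randomisation makes the two groups comparable as assigned. The cage actually implanted is settled later, at operation, by a surgeon who necessarily knows which cage was assigned. If a surgeon departs from the assignment because of the anatomy or the state of the level, the reason may also bear on whether the level fuses. Grouping by implanted cage would then let that decision determine arm membership on the primary endpoint.

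Two consequences follow from a literal reading of Section 4.7.1. A switched subject is counted under the cage received, and a randomised subject who receives neither study cage falls outside both groups. A two-level subject with one cage of each kind has no clear place either. With 35 subjects per arm, a handful of such cases could move the observed fusion difference by several points.

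**Working it through.** **Inputs from the documents.** Section 3.1 gives up to 70 subjects, 35 per group (2 × 35 = 70). No significance level, power, expected fusion rate or dropout rate is given, so the sample size itself cannot be re-derived; this point does not affect it. No switch rate, direction of switching or prognosis of switched subjects is given.

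**Assumptions, for illustration only.** There is no true cage effect. Fusion probability is p in each arm as randomised. Of the 35 subjects assigned to titanium, k receive PEEK instead, and their own fusion probability is q whichever cage they get. Nobody switches the other way.

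**Formulas.**

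- Titanium as implanted: (35p − kq) / (35 − k)
- PEEK as implanted: (35p + kq) / (35 + k)
- Difference: 70k(p − q) / (35² − k²) = 70k(p − q) / (1225 − k²)
- As randomised: p − p = 0

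**Results for p = 0.70, q = 0.30 (35p = 24.5).**

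| k | Titanium as implanted | PEEK as implanted | Spurious difference | As randomised |
|---|---|---|---|---|
| 1 | 24.2/34 = 71.2% | 24.8/36 = 68.9% | 2.3 points | 0 |
| 3 | 23.6/32 = 73.8% | 25.4/38 = 66.8% | 6.9 points | 0 |
| 5 | 23.0/30 = 76.7% | 26.0/40 = 65.0% | 11.7 points | 0 |

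**Sensitivity to the assumptions.**

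- *Rates.* With k = 3, p = 0.60 and q = 0.40, the difference is 210 × 0.20 / 1216 = 3.5 points. With p = 0.80 and q = 0.30, it is 210 × 0.50 / 1216 = 8.6 points.
- *Prognosis.* If q = p, the factor (p − q) is zero and so is the bias. If switched subjects have better prospects than average (q > p), the sign reverses.
- *Direction.* If the switches go from PEEK to titanium, the same figures appear in favour of PEEK. If equal numbers with the same q switch each way, both groups return to 35 subjects with 35p expected fusions, and the bias is zero.
- *No study cage.* If k titanium-assigned subjects with fusion probability q are left out instead of moved, the titanium rate exceeds p by k(p − q)/(35 − k). At p = 0.70 and q = 0.30 this is 0.4/34 = 1.2, 1.2/32 = 3.8 and 2.0/30 = 6.7 points for k = 1, 3 and 5.

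**Type I error.** This was simulated with a pooled two-proportion z-test, an assumed two-sided 0.05 level and 400,000 replicates, with the same mix of prognosis in both arms. At p = 0.70, q = 0.30 and three one-way switches, the rejection rate is about 0.09 by implanted cage and 0.04 as randomised. If switched subjects fuse at 0.70 like the rest, both are about 0.05.

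**The case against.** The strongest reply is that a loosely drafted sentence is being read as a rule. Section 4.7.1 is a success-criteria section and does not set out to define analysis populations. It speaks of either titanium cage although only one is studied. Like Section 2.2, it seems to assume that the assigned and the implanted cage are the same. Elsewhere the plan leans towards randomised groups: Section 4.2 refers to a subject's group status in the same paragraph as randomisation, Section 3.1 gives the number per group, and Section 6 compares the groups.

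Much of this stands. A reader might infer that the plan has deliberately chosen an as-treated primary analysis in which switched subjects change arm and subjects without a study cage are dropped. The documents do not support that: neither event is mentioned, and both are inferences from one phrase. But the leaning elsewhere does not settle the matter. The plan never defines a group as the assigned group for analysis, and an analyst following the one explicit sentence would compare by implanted cage.

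The objection to the size of the effect also stands. The illustration makes every switch go one way and gives switched subjects poor prospects. The documents offer no reason why a difficult case would favour PEEK over titanium. Exclusion criterion 4 (Section 3.3) removes osteoporosis and bone absorption, which narrows the scope for switches prompted by poor bone.

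Finally, rewording the comparison does not by itself deal with a subject whose surgery is cancelled. That subject has no 6-month post-operative outcome under either grouping, so a separate rule is needed.

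**Conclusion.** The concern holds as one of ambiguous wording and an unstated analysis population. On its literal terms, the only sentence defining the primary comparison gives an as-treated analysis in a randomised trial, and no other section says otherwise.

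The size of any bias cannot be known from the documents. The figures of 2.3, 6.9 and 11.7 points depend wholly on the assumed one-way switching by subjects with a poor chance of fusion. The bias is zero if nobody switches or, with no cage effect, if switching is unrelated to prognosis or balanced between arms; otherwise it can favour either cage. A reader might take the illustration as evidence that the plan favours titanium or that its result will be invalid; it shows neither.

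Comparison by assigned cage is nevertheless the better method and costs almost nothing. Severity: should-fix, with moderate confidence; a cheap improvement.

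**What to change.** 1. Reword the comparison in Section 4.7.1 along these lines: *The primary comparison is the proportion of subjects graded BSF-3 at 6 months among those randomised to the titanium cage versus those randomised to the PEEK cage. Each subject is analysed in the assigned group whatever cage is implanted, including two-level constructs with mixed cages.*
2. Repeat in Section 6 that the groups are the randomised groups and that all randomised subjects belong to the primary comparison.
3. State how a randomised subject with no 6-month fusion outcome (for example, surgery cancelled) is counted, in the same way for both arms, and reconcile that rule with the statement in Section 4.8 on withdrawals that are not counted.
4. Report the as-implanted comparison only as a sensitivity analysis. This relies on the instrumentation field collected under Section 4.3. The case report forms are not in the text available for review, so confirm that the field records the cage at each level and add that detail if it does not.

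The cost is a few sentences, and possibly one form field. The planned sample size is unchanged. The downside is that, if switches occur and the cages truly differ, the as-randomised estimate is slightly diluted towards no difference.
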